Cover page for Clinical Trials Document

Study title	Establishment of Reference Intervals of Complete Blood Count and Coagulation Tests in Pregnant Women at Hung Vuong Hospital
NCT Number	NCT05929326
Document date	August 27, 2023

I. STUDY PROTOCOL

Reference intervals are defined as the 2.5th percentile to 97.5th percentile of a normal population. Therefore, it is common to interpret results as abnormality based on normal reference intervals in pregnant women due to their biophysiological changes [1]. As a result, it is crucial to define normal reference intervals for pregnant women. Complete blood count and coagulation tests such as activated partial thromboplastin time (APTT), prothrombin time (PT), and fibrinogen are of a routine hematology panel. There have been many studies conducted on Asian pregnant women [2, 3], but none was conducted in Vietnam. Therefore, we conduct this study to determine trimester specific reference intervals for healthy pregnant women.

Patient selection

From June 2023 to August 2023, pregnant women visiting obstetrics clinics at Hung Vuong Hospital are selected if eligible after history taking and clinical examination. Inclusion criteria was singleton pregnancy. Exclusion criteria were hypertension, diabetes, pre-eclampsia, gestational diabetes, hemoglobinopathy, current infection, positive screening for *treponema pallidum*, hepatitis B virus, HIV, usage of anticoagulant drug. Each patient will have their blood drawn 4 millimeters (mL), 2 mL into citrate anticoagulated tube to test for APTT, PT, fibrinogen, and 2 mL into Ethylenediaminetetraacetic acid (EDTA) tube to test for complete blood count.

To establish reference intervals using non-parametric method, the minimum sample size needed is 120, according to CLSI EP28-A3c [4], because of the 90% confidence interval reported for the 2.5th percentile. However, Sample Sizes for Clinical, Laboratory and Epidemiology Studies [5] suggested a calculation for larger minimum required sample size

$$N_{Rank} = \eta \sqrt{3} \times \left[\frac{z_{1-\gamma/2}}{\rho_{plan} \times z_{1-\gamma/2}} \right]^2 \text{ where } \eta = \frac{\sqrt{(\gamma/2)[1-(\gamma/2)]}}{\phi_{1-\gamma/2}} = 2.11 \quad (\phi_{1-\gamma/2} = \frac{1}{\sqrt{2\pi}} e^{\frac{z_{1-\gamma/2}^2}{2}})$$

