with $\alpha = 0.05$, $\gamma = 0.1$. ρ_{plan} is margin of error, which is the estimate of the percentage that the width of the confidence interval of the reference limits is of the width of the reference interval. The recommended ρ_{plan} is 10%. From the formula above, the calculated sample size required is 258 patients. Because we want to establish trimester specific reference intervals, the total combined number of each trimester is at least 774 patients.

Ethical approval

The study was approved by the Ethical committee of Hung Vuong Hospital, Vietnam. Written consent was obtained before study participation.

Samples collection and instrument

Venous blood samples were collected in trisodium citrate 3.2% and K₂EDTA plastic whole blood tube and then immediately analyzed.

Instrument and analysis

Coagulation assays, which comprises of Activated partial thromboplastin time (APTT), prothrombin time (PT), fibrinogen (FIB), was performed on ACL TOP 550 automated coagulation analyzer (Werfen, Barcelona, Spain) and complete blood count, including White blood cell (WBC) counts and percentage and absolute count of different

leukocytes (neutrophils, lymphocytes, monocytes, eosinophils and basophils), red blood cells (RBC), hemoglobin (Hgb), hematocrit (HCT), mean corpuscular volume (MCV), mean corpuscular hemoglobin (MCH), mean corpuscular hemoglobin concentration (MCHC), RBC distribution width (RDW), platelet counts (PLT), mean platelet volume (MPV), was performed on DxH900 automated hematology analyzer (Beckman Coulter, CA, USA).

All instruments were maintained and calibrated according to the manufacturer's instruction. Two levels of controls were done on ACL TOP 550 analyzer every eight-hour shift and three levels of controls were run DxH900 once a day.

II. STATISTICAL ANALYSIS PLAN

Patients are divided into three groups, based on their gestational age. The three groups are the first, second and third trimester. The non-parametric method, recommended to establish reference intervals by CLSI EP28-A3c, is used to determine the lower reference limit 2.5th percentile and upper reference limit 97.5th percentile for each group. Each reference limit was reported along with its 90th confidence interval. Groups are then compared using Mann-Whitney U and Kruskal-Wallis tests. A two-tailed P-value < 0.05 was considered significant.

REFERENCES

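### Do the unordered Kruskal-Wallis and Mann-Whitney tests at P < 0.05 need a stated gate or a multiplicity adjustment?

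*Combined protocol and SAP*

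**What the plan says.** The aim, in the introduction to the Study Protocol, is estimation: "Therefore, we conduct this study to determine trimester specific reference intervals for healthy pregnant women".

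The Statistical Analysis Plan fixes the groups in advance ("The three groups are the first, second and third trimester") and sets non-parametric 2.5th and 97.5th percentile limits for each, with confidence intervals. Testing comes after that, in two sentences: "Groups are then compared using Mann-Whitney U and Kruskal-Wallis tests" and "A two-tailed P-value < 0.05 was considered significant". Nothing is said about test order, pairs, analytes or adjustment.

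The panel is listed under Instrument and analysis: three coagulation tests and a complete blood count that includes percentages and absolute counts of "leukocytes (neutrophils, lymphocytes, monocytes, eosinophils and basophils), red blood cells (RBC), hemoglobin (Hgb), hematocrit (HCT") and further red-cell and platelet indices.

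The sample size, under Patient selection, is derived from the precision of the limits: "From the formula above, the calculated sample size required is 258 patients", so that "the total combined number of each trimester is at least 774 patients".

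**The concern.** Mann-Whitney U compares two groups and the plan has three, so its use implies pairwise testing. Three pairwise tests at 0.05 do not hold a 5% error for one analyte unless something controls them, and the text names no control. Mann-Whitney is also named before Kruskal-Wallis, so the wording itself does not establish a gate.

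The panel multiplies the opportunities. With 23 analytes, one Kruskal-Wallis test and three pairwise tests each, there could be 23 × (1 + 3) = 92 tests at the same threshold, with no adjustment and no exploratory label. A reported trimester difference in an analyte that does not change in pregnancy could then be chance, and the choice of pairs could be made after seeing the data. At stake is the credibility of statements that a given analyte differs between trimesters.

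**Working it through.** **The plan's own figure.** Inputs from Patient selection: α = 0.05, γ = 0.1, margin of error 10%.

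- η = √(0.05 × 0.95) / φ(1.645) = 0.2179 / 0.1031 = 2.113, against the stated 2.11.
- N = η√3 × [1.645 / (0.10 × 1.960)]² = 3.660 × 70.4 = 257.8, so 258 per trimester, and 3 × 258 = 774.

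This takes the denominator z at 1 − α/2 and a negative exponent in φ. The printed formula differs on both, but the stated 258 and 2.11 come from these forms. No input is an error rate for comparing trimesters.

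**Panel size.** 3 coagulation tests + WBC + 5 leukocyte percentages + 5 absolute counts + 9 red-cell and platelet indices = 23.

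**Error for one analyte with no trimester difference.** With equal groups, the largest of the three pairwise statistics is the range of three standard normals divided by √2.

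- All three pairs, no gate: P(range of 3 > 1.96 × √2) = 12.2%. A simulation of the actual rank tests at 258 per group (20,000 runs) gave 12.0%, standard error 0.2 points.
- Two adjacent pairs only, no gate: about 9.1% (normal approximation, simulated).
- Pairwise tests read only after Kruskal-Wallis P < 0.05: 5.0% (rank simulation 4.8%).
- Unequal groups, three pairs, no gate: 12.0% at 120/258/396, 11.9% at 100/100/574, 11.5% at 50/362/362.

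The independence formula, 1 − 0.95³ = 14.3%, overstates the ungated figure because the pairs share groups.

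For three groups the gate is enough within an analyte. If all three are equal, Kruskal-Wallis holds 5%. If exactly one differs, only one true null pair remains, and it is tested at 5%.

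**What control would cost.** Assumptions: normal data, 258 per group, rank-test efficiency 3/π. For a difference of δ SD, the pairwise statistic has mean δ × √(258/2 × 3/π) = 11.10δ.

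- *Gate alone, first versus third, 0.3 SD.* Ungated power is Φ(3.33 − 1.96) = 91.5%. Gated power, by simulation, is 85.0% under a linear trend and 89.7% if only the third trimester shifts.
- *Gate alone, adjacent pair, linear trend totalling 0.4 SD (0.2 SD per step).* Ungated power is Φ(2.22 − 1.96) = 60%. The gate changes it by about 0.1 point, and by under 1 point at 0.3 SD.
- *Gate plus Holm's strictest step, 0.05/23 = 0.0022 (critical value 3.07), same adjacent pair.* Φ(2.22 − 3.07) = 20%, down from 60%. For trends totalling 0.3 and 0.5 SD, power falls from 38% to 8% and from 79% to 39%. Later Holm steps are less strict.

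**Across the panel.** A panel-wide error rate needs the number of unchanged analytes and their correlations. The documents give neither, and no simple model fits: the five leukocyte percentages share one total, absolute counts follow from WBC and the percentages, and red-cell indices derive from one another. I therefore put no weight on a panel-wide figure.

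**The case for a change.** The strongest case for a change is this. The trimester comparison is the only hypothesis test in the plan, and 0.05 is its only inferential rule. A study of trimester-specific intervals will naturally report which analytes differ by trimester. The difference between 12% and 5% arises within a single analyte, so it survives even if multiplicity over the panel is set aside. Stating the gate would take a sentence and cost little power.

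Much of this stands. The omission is in the text, the figures reproduce, and a gate is valid and cheap. It does not show that the plan goes wrong when followed. The 12.2% needs two choices together: all three pairs tested, and Kruskal-Wallis ignored when reading them. The plan specifies neither, and an analyst given both tests and three groups would ordinarily use Kruskal-Wallis overall and Mann-Whitney to locate differences. The plan also promises no 5% rate per analyte or per panel; it states a threshold for a P-value.

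The panel-wide part is weaker. Whether a descriptive comparison needs familywise control is a matter of judgement. Holm would sacrifice much of the ability to see modest steps between adjacent trimesters, and labelling the tests exploratory and unadjusted would leave every P-value and limit as it is.

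**Conclusion.** No change to the plan is needed. The unstated order and pairs are missing detail that analysts fill sensibly, and the lack of adjustment over analytes is a fair trade-off.

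The possible effect is 12.2% against 5.0% for one unchanged analyte if all three pairs are tested ungated, or about 9% against 5.0% for adjacent pairs only. It is confined to a secondary, descriptive comparison. The reference limits, their 90% confidence intervals, the trimester split and the 258 per trimester use no P-value, and no decision in the plan depends on these tests. In particular, the three groups are kept whatever the tests show.

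The error rates assume identical distributions in the three trimesters and large-sample behaviour of the rank tests, which the simulation at 258 per group supports. The power figures assume normal data and the shift patterns shown. The conclusion would differ if P-values decided whether trimesters were pooled or which intervals were issued, but the plan contains no such rule.
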